#### 4.2 Adverse Effects

In this study, adverse effects are defined as undesired effect that occurs medication is administered. We will use Scripted Prompting, a proactive form of adverse effect capture recognized in the field. This method is designed to elicit adverse effects without biasing the patient; it is a standardized question that allows participant to report important symptoms without being influenced by suggestion. For this study we will ask: *“Since initiating medical marijuana are you having any problems related to use?”*

To describe factors associated with adverse effects we will report the number of adverse effects reported by participants at time points 2 and 3. Adverse Effects will be defined as both a count variable and a binary variable such that absence or presence of adverse effects will be coded as 0/1 respectively. We will then use Poisson and Logistic regression methods to examine analyze the bivariate association between dosage, frequency of use, route of administration (pills, vape, etc.), and type of product (THC v. CBD). Limitations may be related to the frequency and distribution of events leading to complete or quasi-separation of data points. Possible mitigations would be re-categorization of explanatory variables, exact or firth regression, or a different functional form of the model.

PROTOCOL TITLE: Medical Marijuana Use and Driving Performance: A Test of Psychomotor Function in Adults 50 and Older.

## 5.0 Study Intervention

### 5.1 Type: Drug

Name: Medical Marijuana

Description: Medical marijuana is defined by Florida state statute 381.986 as all parts of any plant of the genus Cannabis, whether growing or not; the seeds thereof; the resin extracted from any part of the plant; and every compound, manufacture, salt, derivative, mixture, or preparation of the plant or its seeds or resin, including low-THC cannabis, which are dispensed from a medical marijuana treatment center for medical use by a qualified patient.

This protocol describes an assessment of Medical Marijuana Use and Driving Performance: A Test of Psychomotor Function in Adults 50 and Older. Sixty participants will be recruited from Medical Marijuana Treatment Clinics (MMTC) of Gainesville. The intervention group will be comprised of adults 50 and older who report severe or chronic pain, are newly registered for the Medical Marijuana Registry in the State of Florida, have no prior history of medical marijuana use, can communicate in English, and are willing and able to complete study procedures. The control group will be age, gender, and race matched. The primary study outcome is simulated driving performance (i.e. errors in response time, attention, and executive functioning tasks that predict on-road performance). Secondary outcomes include adverse effects.

## 6.0 Procedures Involved\*

\* NOTE: To minimize risk of exposure to COVID-19, we will initially only recruit participants age 50 and older. Any portions of the study that can be conducted via videoconference, such as the informed consent process, will be conducted via videoconference. HIPAA protected Zoom software provided by FSU will be used for videoconferences. FSU Qualtrics will be used for virtual informed consent. Participants who are consented virtually will be mailed a copy of the informed consent. Participants who are consented virtually will also be offered a copy of the informed consent when they arrive for baseline assessments. Appointments will be scheduled so that no overlapping appointments occur among participants in order to minimize exposure. No person who has been exposed to Coronavirus or who is at higher risk for severe illness may take part in our study. Severe illness means certain health conditions related to your heart, liver, or lungs, or if you have diabetes. Also, persons who live in nursing homes, have severe obesity, or who have immune disorders may not take part in this study. There may be other conditions, and this list may change.

PROTOCOL TITLE: Medical Marijuana Use and Driving Performance: A Test of Psychomotor Function in Adults 50 and Older.

We will ask some questions to see who may be at risk of severe illness. We will also ask people to see if they have been exposed to Coronavirus. If you think that you may have been exposed to Coronavirus or have a severe illness, let us know. Study staff may or may not include licensed medical doctors, and may not be able to give you any medical advice on your Coronavirus risk. Please talk to your doctor if you have questions about your own risk. Information about persons who may be at risk can be found at the following website:

<https://www.cdc.gov/coronavirus/2019-ncov/need-extra-precautions/groups-at-higher-risk.html>.

We will make sure that at all times everyone stays a safe distance from one another. This is called “social distancing.” We follow the rules about use of equipment to protect you. This includes masks, gloves and other equipment. If needed we will supply these to you. You must wear these in order to take part in this part of the study. If study staff need to be close to you, we will take all the steps needed to protect you. We follow the rules about use of equipment to protect you. This includes masks, gloves and other equipment. If needed we will supply these to you. You must wear these in order to take part in this part of the study. If study staff need to be close to you, we will take all the steps needed to protect you. We will limit the number of people in any face-to-face activity. We will also limit the amount of time that anyone has a face-to-face activity. Only the least amount of people and time will be used in this study.

If at any time you don't feel safe with the steps that we will take to protect you, please let us know and we will stop. We want to be sure to answer your questions and to take any other steps that you feel we should take to protect you.

6.1 Recruitment/Sampling. We will recruit patients using from Medical Marijuana Treatment Clinics (MMTC) of Gainesville. Patients who complete the process of being entered into the medical marijuana registry and meet study inclusion criteria will be informed about the study during their initial visit to their prescribing physician. Recruitment for this study begins pre-medical marijuana exposure. Once a patient has obtained their official card from the state of Florida, the baseline assessment will be scheduled and completed prior to the patient's first dispensation of marijuana. After patients have filled their first prescription, we will track patients through MMTC and follow patients for 3 months post medical marijuana initiation, using both in person visits and EMR abstraction.

We will recruit N=60 participants total. Participants will be eligible for the current study if they: a) report severe or chronic pain; b) are age 50 or older; c) are newly registered for the Medical Marijuana Registry in the State of Florida; d) have no prior history of medical marijuana use; e) can communicate in English; and f) are willing and able to complete study procedures or if they meet control group criteria: (n=30) Medical Marijuana Users **or** (n=30) Age, Gender, Race Matched Controls. Persons will be ineligible if they: a) meet

**PROTOCOL TITLE:** Medical Marijuana Use and Driving Performance: A Test of Psychomotor Function in Adults 50 and Older.

criteria for current or past alcohol and/or illicit drug dependence; b) have vertigo or any vestibular systems dysfunction (due to the to develop simulator adaptation syndrome); c) screen high on the simulator sickness prescreen; d) use contraindicated medication (benzodiazepines, beta blockers, antihistamines, or sedatives) from which they cannot abstain due to medical reasons; and/or e) are planning to move out of the area within 6 months.

We will recruit patients in the control group within the local community. This will happen by placing recruitment flyers in public places (i.e. grocery stores, libraries, senior living communities, etc.). Additionally, we will utilize Consent2Share, an initiative of the UF Integrated Data Repository (IDR) and supported by UF CTSI (Clinical and Translational Science Institute) that allows for a large group of potential research participants who have consented to be re-contacted for future research studies. The control group will be matched by age, gender and race. Control subjects will be ineligible if they: a) meet criteria for current or past alcohol and/or illicit drug dependence; b) have vertigo or any vestibular systems dysfunction (due to the to develop simulator adaptation syndrome); c) screen high on the simulator sickness prescreen; d) use contraindicated medication (benzodiazepines, beta blockers, antihistamines, or sedatives) from which they cannot abstain due to medical reasons; and/or e) are planning to move out of the area within 6 months, f.) have a history of marijuana use. Control subjects will be used to ensure results are not attributed to a simple change in time. Results will provide evidence for the effects of medical marijuana use on the real work task among adults 50 and older.

**6.2 Baseline Assessment Procedures.** Once eligibility has been met, participants will be scheduled for their baseline assessment in the week prior to starting medical marijuana. At the baseline appointment, participants will be greeted by a study research assistant who will introduce the study and provide the patient with informed consent. We have standardized the informed consent procedure to ensure that participants not only understand the informed consent process but also fully understand what is being asked of them during the study period. Following informed consent, participants will complete the baseline assessment. The baseline assessment will consist of a battery of psychosocial measures, a cognitive test, a 5 minute simulator adaptation drive, and a 15 minute main drive. Adherence to simulator sickness protocol will be ensured before, during, and after the drives. In an effort to maintain engagement, participants will be contacted via telephone 60 days post-baseline to complete a 3-item questionnaire regarding significant life changes as well as a pain scale. We will also request permission to extract needed data on an ongoing basis from patients' electronic medical records.

**6.3 Training of Research Assistants.** All study research assistants will be trained in Good Research Practices, Safety Concerns in Dealing with Patients, and Data Collection Procedures. The training will also cover 1) familiarization with study aims, instruments, and assessment procedures specific to the study; 2) confidentiality and informed consent, data integrity, and data security; 3) observation of mock assessment conducted by the project director; and 5) a

PROTOCOL TITLE: Medical Marijuana Use and Driving Performance: A Test of Psychomotor Function in Adults 50 and Older.

practice assessment with the project director. Research assistants will also receive “red flag” training on how to recognize and respond to danger to self and others, child abuse, elder/dependent adult abuse, and domestic violence.

Several procedures will help standardize data collection and encourage accuracy and honesty in reporting, as follows: 1) trained research assistants will conduct the assessments; 2) a private interview setting will minimize distractions and ensure confidentiality; and 3) research assistants will remind participants of the confidentiality of the information that they provide.

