## **17.0 Data Management\* and Confidentiality**

17.1 **Test of Aim 1 (Driving Simulator):** Between group (medical marijuana users vs controls) comparisons will first be examined using independent samples t-test (controlling for unequal variances using Levene's test) or Mann-Whitney U tests if the data are nonparametric. Repeated measures ANOVA will be used to examine within participants differences on measures at all 3 time points in order to answer the question of whether medical marijuana impacts response time, divided attention, and executive functions.

Limitations may be related to the distribution of the dependent and independent variables. Possible mitigation approaches include creating a dichotomous variable of high versus low for outcomes and using logistic regression or other functional form as dictated by the distribution of the dependent and independent variables.

17.2 **Test of Aim 2 (Adverse Effects):** To describe factors associated with adverse effects we will report the number of adverse effects reported by participants at time points 2 and 3. Adverse Effects will be defined as both a count variable and a binary variable such that absence or presence of adverse effects will be coded as 0/1 respectively. We will then use Poisson and Logistic regression methods to examine analyze the bivariate association between dosage, frequency of use, route of administration (pills, vape, etc.), and type of product (THC v. CBD). Limitations may be related to the frequency and distribution of events leading to complete or quasi-separation of data points. Possible mitigations would be re-categorization of explanatory variables, exact or firth regression, or a different functional form of the model. The goal of aim 2 is to examine the strength of the association between factors of medical marijuana use and adverse effects. As there may be insufficient power for statistical

PROTOCOL TITLE: Medical Marijuana Use and Driving Performance: A Test of Psychomotor Function in Adults 50 and Older.

significance, effect size estimates (Cohen's d) will be used to examine the strength of the association between variables.

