### 17.7 Data and Safety Monitoring Activities

17.7.1 The data collected by the current project presents low to minimal risk to participants. Participants will be asked to answer a set of questionnaires, provide a urine specimen which will be used to detect the presence or absence of THC and other drugs, and participate in an approximately 20 minute simulated drive. Participants who meet criteria for current or past alcohol and/or illicit drug dependence, have vertigo or any vestibular systems dysfunction (due to the risk to develop simulator adaptation syndrome), screen high on the simulator sickness prescreen (a score of 13 or greater), use medications as identified by the

PROTOCOL TITLE: Medical Marijuana Use and Driving Performance: A Test of Psychomotor Function in Adults 50 and Older.

referring physicians that would negatively impact mental or physical functioning due to side effects, or have a diagnosis of severe psychiatric (e.g., psychoses) or physical conditions (e.g., missing limbs) that would preclude full participation will be excluded from the study. Further, vulnerable populations will not be enrolled in the current trial.

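### As written, no Aim 1 test compares users with controls using T1, and the power in 17.4 rests on an average that includes the pre-exposure visit

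*Combined protocol and SAP*

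**What the plan says.** Purpose of the controls (6.1): "Control subjects will be used to ensure results are not attributed to a simple change in time".

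Aim 1 analysis (17.1): the between-group "comparisons will first be examined using independent samples t-test", or a Mann-Whitney test. No visit, change score or T1 adjustment is given. Then: "Repeated measures ANOVA will be used to examine within participants differences on measures at all 3 time points". This ANOVA is the step that is to answer whether marijuana affects the three driving domains. No group factor or group-by-time term is named, and it is not said whether users alone or all 60 enter it.

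Power (17.4): 0.5 SD between groups in the average of three visits, correlation 0.2, SD of the average 0.683, 31 per group, two-sided, 80% power. Alpha is not stated. Section 6.1 plans 30 per group.

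Groups (6.1): users report severe or chronic pain and "have no prior history of medical marijuana use". Controls are matched on age, gender and race, have no pain criterion, and are ineligible if they "have a history of marijuana use". Dependence is excluded in both groups. Section 6.1 also states: "Recruitment for this study begins pre-medical marijuana exposure". Section 17.7 says participants will "provide a urine specimen which will be used to detect the presence or absence of THC and other drugs", without naming a visit or an analysis.

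**The concern.** To show that a change is not merely the passage of time, the change in users has to be set against the change in controls. Neither written test does this.

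- A within-participant ANOVA removes stable differences between people but keeps any change that time produces. Section 6.11 repeats the same main drive at each visit, so practice is possible. A practice gain could hide an impairment, and a decline over time could mimic one.
- A users-versus-controls test on levels removes a time change that both groups share but keeps any stable difference between them. The entry rules leave room for such a difference in pain and in non-medical marijuana use.

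Separately, the three-visit average in 17.4 includes T1, before any user has been dispensed marijuana. If the effect begins after T1, averaging in T1 dilutes it, and the 80% does not apply to the question that Aim 1 asks.

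**Working it through.** **Inputs.** From the plan: correlation 0.2 (called r below), difference 0.5 SD, two-sided (17.4); 30 per group (6.1). Assumed: alpha 0.05, equal correlation between all visits, SD of one measure = 1, and every time or group shift below. Power is from the noncentral t distribution with 58 df and noncentrality difference / (SD × sqrt(2/30)).

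**1. The plan's own figure.** SD of the three-visit average = sqrt((1 + 2×0.2)/3) = 0.683, as stated. For 0.5 SD in that average the t calculation needs 30.3, so 31 per group. It reproduces. Power is 81% at 31 and 80% at 30 per group.

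**2. Effect present only at T2 and T3.** Difference in the average = (0 + 0.5 + 0.5)/3 = 0.333 SD. Noncentrality = 0.333/(0.683 × 0.258) = 1.89. Power is 46%; 80% would need 67 per group.

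**3. Tests that use T1, for 0.5 SD at T2 and T3.**

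- Change contrast, mean(T2,T3) − T1: SD = sqrt((1+r)/2 + 1 − 2r). At 0.2 this is sqrt(1.2) = 1.095.
- T1-adjusted mean(T2,T3): SD = sqrt((1+r)/2 − r²). At 0.2 this is sqrt(0.56) = 0.748.

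| Correlation | Change contrast | T1-adjusted | Share of a stable difference left by T1 adjustment (1 − r) |
|---|---|---|---|
| 0.2 | 41% | 72% | 80% |
| 0.5 | 59% | 77% | 50% |
| 0.6 | 69% | 82% | 40% |

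At 0.2, 80% power needs 77 per group for the change contrast and 37 for the T1-adjusted test. The omnibus group-by-time F test (2 and 116 df) has noncentrality 15 × (2/3) × 0.25/0.8 = 3.125 and about 33% power.

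**4. Time change shared by both groups, no drug effect.** For a shift s at T2 and T3, the one-way ANOVA has noncentrality n × (2/3) × s²/(1 − 0.2). In 30 users this is 0.25, 1.0 or 2.25 for s = 0.1, 0.2 or 0.3 SD, and the test is significant 7%, 13% or 24% of the time. In all 60 pooled it is 9%, 22% or 45%. The change contrast stays at 5%. Masking: with a true 0.5 SD impairment and a practice gain of 0.2 or 0.3 SD, the net shift is 0.3 or 0.2 SD. The users-only ANOVA falls from 58% to 24% or 13%; the change contrast keeps 41%.

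**5. Stable group difference, no drug effect.** For 0.1, 0.2 or 0.3 SD the three-visit average is significant 9%, 20% or 39% of the time, the T1-adjusted test 7%, 13% or 23% (6%, 8% or 13% at correlation 0.5), and the change contrast 5%. As a plausibility check on pain, if all users and a share q of controls have pain, the pain effect needed is shift/(1 − q). With q of 35–52% (Section 3.1), a 0.2 SD shift needs 0.31–0.42 SD. A 0.3 SD shift needs 0.46–0.63 SD, close to the Parkinson comparison in 17.4 (0.46–0.65), so it is an extreme case.

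**The case against.** The strongest reply is that a two-group repeated measures ANOVA is meant. Section 17.1 starts from users versus controls and moves on to all three visits, and 6.1 says why controls exist. That is plausible, so the supported statement is that the comparison is not written down, not that the wrong test was chosen; step 4 applies only if group is left out. It does not rescue 17.4, which powers a different quantity.

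A reader might also infer that the eligibility rules are themselves the defect, or that users' T1 is contaminated by earlier use. The documents do not show this. They give no share of users with recent non-medical use, a urine THC test is planned, the baseline battery is not itemised, and the figure after 6.11 is not available, so T1 data on use and pain may already be collected.

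Nor is confounding by pain established. Controls with pain are not barred. Section 6.0 excludes several serious health conditions, 6.1 excludes sedating and other listed medicines, and 17.7 excludes people on medicines named by "referring physicians that would negatively impact mental or physical functioning due to side effects". Practice may be reduced by the adaptation drive and by random presentation of events (6.7).

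Finally, one could read the change contrast as the only valid choice. It is not: it removes a stable difference fully but has 41% power at the plan's correlation, whereas T1 adjustment has 72% and leaves part of the difference in place.

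**Conclusion.** The point holds for 17.1 and 17.4. No written Aim 1 test both uses T1 and compares the groups, so the stated purpose of the controls is not delivered by the text. The firmest figure concerns power: for 0.5 SD arising after T1, the quantity powered in 17.4 has about 46% power at 30 per group, not 80%. This rests on the plan's correlation of 0.2, an assumed alpha of 0.05 and an equal effect at T2 and T3.

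The error rates in steps 4 and 5 are illustrations: the documents give no size for practice, pain or prior use. The differing marijuana-history rules and the pain requirement are reasons to expect a possible stable difference, not proof of one. Neither recommended test removes time trends that differ between the groups, and neither repairs a T1 that is already marijuana-exposed.

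**What to change.** 1. In 17.1, name one between-group test that uses T1 as the Aim 1 test: either the group-by-time contrast (mean of T2 and T3 minus T1, users versus controls) or the T1-adjusted comparison of T2/T3. Make the other a sensitivity analysis. For the yes/no executive-function items, name a matching model for repeated binary data. Say when controls have T2 and T3, since 6.11 times these visits from first dispensing.
2. In 17.4, restate the power for the chosen test at 30 per group, over a range of correlations as in the table, and state alpha. If the T1-adjusted test is chosen, say that it leaves a share of 1 minus the correlation of any stable group difference.
3. As a minor addition, state that the planned urine THC test is done at T1, and add a sensitivity analysis without T1-positive participants. For the change contrast at correlation 0.2, power is about 39%, 37% or 32% if 3, 6 or 12 users are set aside. Report pain at T1 for description only. Eligibility stays as it is.

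The cost is wording in 17.1 and 17.4, plus a T1 urine test and a short pain scale if these are not already in the baseline visit. The real price is an honest power figure, which at correlation 0.2 is below 80% for either test.

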6.8 Adverse Effects: In this study, adverse effects are defined as undesired effect that occurs when the medical marijuana is administered. We will use Scripted Prompting, a proactive form of adverse effect capture recognized in the field. This method is designed to elicit adverse effects without biasing the patient; it is a standardized question that allows participant to report important symptoms without being influenced by suggestion. For this study we will ask: "*Since initiating medical marijuana, are you having any problems related to use?*"

6.9 Control Procedures: Control participants will be community-dwelling age, race, and gender matched.

6.10 Participant Retention: We will develop a strong collaborative relationship between participants and members of the research team through empathy, encouragement and skill building.

6.11 Three- and Six-Month Follow-Up Assessment: The second assessment (T2) will occur one month after the participant has been dispensed medical marijuana for the first time. T3 will occur 3 months after the participant has been dispensed medical marijuana for the first time. The follow-up assessments will consist of a minimally reduced psychosocial assessment battery, and the same simulator adaptation and main drive (described above). All participants will be paid \$50 per assessment visit (\$150 total across all visits over the 3 month period). Participants

**PROTOCOL TITLE:** Medical Marijuana Use and Driving Performance: A Test of Psychomotor Function in Adults 50 and Older.

will not be paid for screening assessments or chart abstracted data. Data will be collected using both self-directed methods such as ACASI with headphones or self-administered on paper and Research Assistant administered tasks. The Baseline Assessment is expected to take approximately 90 minutes, and follow-ups will take approximately 60 minutes. Though it is time-consuming, we do not anticipate participant barrier as a burden based on prior work.

[figure not shown]

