## **14.0 Withdrawal of Subjects\***

14.1 The Principal Investigator can withdraw participants from this study for unanticipated reasons.

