### 17.5 Missing Data

17.5.1 We will handle missing data values with a 3-step process. First, the dropout rates will be compared across the groups with chi-square analyses to assess systematic differences due to condition. Second, demographic and dependent variables will be examined for their relationship to dropout. Those variables related to dropout status will be used to impute missing values for use in the analyses described (via SPSS Missing Items Analysis). Finally, comparison of the completers vs. imputation analyses will yield an additional estimate of the effect of dropouts on hypothesis tests.

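### Users who leave before T2, or who leave with a new effect after T2, have no planned adverse-effect record, and effects that have resolved by the visit may be missed

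*Combined protocol and SAP*

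**What the plan says.** - **Outcome.** The Study Summary names adverse effects as the only secondary objective, and they are the whole outcome of Aim 2 (section 2.0).
- **Capture.** Sections 4.2 and 6.8 give one scripted question: "Since initiating medical marijuana are you having any problems related to use".
- **Reporting.** Section 17.2: "we will report the number of adverse effects reported by participants at time points 2 and 3". The coding is "Adverse Effects will be defined as both a count variable and a binary variable".
- **Visit timing (6.11).** "The second assessment (T2) will occur one month after the participant has been dispensed medical marijuana for the first time". The final visit is timed from the same event, at 3 months.
- **Contact between visits (6.2).** As an engagement measure, the plan states: "participants will be contacted via telephone 60 days post-baseline to complete a 3-item questionnaire regarding significant life changes as well as a pain scale".
- **Withdrawal (14.1).** The whole section reads: "The Principal Investigator can withdraw participants from this study for unanticipated reasons". It plans no exit contact, no recorded reason for leaving and no final adverse-effect question.
- **Missing data (17.5).** Dropout is compared across groups, and then "Those variables related to dropout status will be used to impute missing values". Completer and imputed analyses are compared at the end.

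**The concern.** The planned adverse-effect data depend on the user attending T2 or T3. Suppose a user feels unwell in week 2, stops and does not return. Nothing in the plan records the effect or the reason for leaving. Likewise, a user with nothing to report at T2 who then has an effect and leaves stays on file as effect-free. A user who stopped and still attends is asked, but the wording asks about problems the person is having, so an effect that has already cleared may not be mentioned.

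Effects serious enough to make someone leave are among those Aim 2 most needs to count. If leaving is related to effects, the reported rate is too low. If that loss also differs by product, route or dose, the associations under H2a to H2c are distorted.

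**Working it through.** **1. Is there another route by which the effect would be recorded?**
- Electronic record abstraction (6.1, 6.2) runs over the 3 months, but adverse effects are not named as an item to extract or as a source for the counts in 17.2.
- Registry dispensary data (6.6) give dosage, frequency, product and route. They show part of the pattern of use, but not why it stopped or exactly when.
- The urine THC test (17.7) has no stated timing and gives no reason for stopping.
- The staff problem form (17.6, 17.9) covers occurrences during data collection, so it does not reach someone who stays away.

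None of these is named as a source of adverse-effect counts.

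**2. Where does the 60-day call fall?** Baseline is in the week before starting. T2 is then at about day 30 to 37 after baseline and T3 at about day 90 to 97. The call at day 60 comes after T2 and before T3.

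**3. How large could the effect be?** The plan gives no adverse-effect rate, dropout rate or sample-size calculation for Aim 2 (17.4 concerns driving only), so there is no planned figure to reproduce. The inputs below are assumptions, except the 30 users (6.1):
- 15 THC and 15 CBD users, with true risks of 50% and 25%.
- Affected: 7.5 + 3.75 = 11.25 (37.5%). Unaffected: 7.5 + 11.25 = 18.75.
- True odds ratio: (7.5/7.5)/(3.75/11.25) = 3.0.
- 5% of unaffected users leave in each product group, so 18.75 × 0.95 = 17.81 remain.
- Shares q_T and q_C of affected THC and CBD users leave before being asked.

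Observed rate = seen/(seen + 17.81), where seen = 7.5(1 − q_T) + 3.75(1 − q_C). Observed odds ratio = 3.0 × (1 − q_T)/(1 − q_C).

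| q_T, q_C | Cases seen | Observed rate | Odds ratio |
|---|---|---|---|
| 20%, 20% | 6 + 3 = 9 | 33.6% | 3.0 |
| 40%, 40% | 4.5 + 2.25 = 6.75 | 27.5% | 3.0 |
| 40%, 10% | 4.5 + 3.375 = 7.875 | 30.7% | 3.0 × 0.6/0.9 = 2.0 |
| 60%, 20% | 3 + 3 = 6 | 25.2% | 3.0 × 0.4/0.8 = 1.5 |

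**4. When is there no bias in the rate?** If affected and unaffected users leave equally often, the share is unchanged. With a true share of 40% and 10% of each leaving, it is 0.36/(0.36 + 0.54) = 40%, although 1.2 of 12 affected users are still unrecorded.

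**5. Does imputation repair it?** Suppose leavers are imputed at the rate seen among stayers on the same product.
- At 40% versus 10%, stayer rates are 4.5/11.625 = 38.7% and 3.375/14.0625 = 24.0%. Their average is about 31%, and the odds ratio is still 2.0.
- At 60% versus 20%, they are 3/10.125 = 29.6% and 3/13.6875 = 21.9%. Their average is about 26%, and the odds ratio is still 1.5.

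The completer and imputed analyses would agree closely, and both would be biased.

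**The case against.** - **Quitting is not leaving.** A reader might infer that everyone who stops the product goes uncounted. The documents do not support that. A user who stops but attends is asked with a look-back to initiation, and an effect reported at T2 is counted even if the user then leaves. The present-tense wording is the only risk for users who attend.
- **Follow-up does not rest on visits alone.** Records, registry data and the urine test track users between visits, and 6.11 pays $50 per visit to support attendance. Because use is partly tracked elsewhere, its absence from the call is a smaller gap than the absence of effects.
- **The T2 and T3 restriction is partly inferred.** It rests on the reporting sentence. Section 6.8 gives no schedule for the question, the three call items are not listed, and the figure after 6.11 is not shown. As the text stands, though, no other occasion is named.
- **Dropout is not ignored.** Section 17.5 compares dropout by group, imputes, and compares completers with imputed results. That is fair, but none of these steps can supply an effect that was never recorded.
- **Aim 2 is imprecise anyway.** In the assumed table the standard error of the log odds ratio is √(1/7.5 + 1/7.5 + 1/3.75 + 1/11.25) = 0.79. The 95% interval around 3.0 is therefore about 0.6 to 14, and a shift to 2.0 lies well inside it. This limits the priority of the point. However, 17.2 concedes low power and relies on effect sizes for that reason, and selective loss biases the effect size.

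**Conclusion.** The point holds in a limited form. The gap covers users who leave before T2, users who have a new effect after T2 and then leave, and possibly users who attend after an effect has resolved. It would be tempting to say that the reported rate is too low. That follows only if affected users leave more often than others, and the documents give no rate from which to judge it. Distortion of the Aim 2 associations further requires that this loss differ by product, route or dose. The odds ratios of 2.0 and 1.5, against a true 3.0, illustrate assumed loss rates and are not predictions.

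A reader might also infer that adding items to the 60-day call would be enough. It would not: the call comes after T2, and helps a week-2 leaver only if that person can still be reached. The change is worth making because it is cheap and protects the sole secondary outcome.

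**What to change.** 1. **Main change.** Phone any user who misses T2 or T3, or is withdrawn, unless contact is refused. Ask the scripted question, worded to cover problems at any time since initiation, and ask whether, when and why use stopped. Using the same wording at T2 and T3 would also catch resolved effects in users who attend and keep the sources comparable.
2. **60-day call.** Add the same items for the user group, to cover the interval between T2 and T3.
3. **Section 17.2.** Use these reports in both outcomes instead of imputing them: binary = 1 if an effect is reported, and the count = number of effects reported. Flag whether each report came by phone or in person.

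Cost: a few short calls and some extra items on a call already planned, with no new visit. Some effects will be reported by phone rather than in person, which is why the mode should be recorded.
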